3.1.5.2 Prior/concomitant vaccines

Based on pre-defined SS, prior/concomitant vaccines will be tabulated.

3.2 Efficacy Analyses

Efficacy analyses will be performed based on the PPS and pre-defined SS, respectively, with the PPS used for the primary analysis and SS used for the supportive analysis. In case of any inconsistency between the actual and the pre-defined groups in the study, sensitivity analyses will be performed based on actual SS.

3.2.1 Primary Efficacy Analysis

3.2.1.1 GMC of RVNA on Day 8 post-dose

3.2.1.1.1 Primary Analysis

Null hypothesis: $\text{GMC}_{\text{SYN023}}/\text{GMC}_{\text{HRIG}} \leq 1.2$.

Alternative hypothesis: $\text{GMC}_{\text{SYN023}}/\text{GMC}_{\text{HRIG}} > 1.2$.

$\text{GMC}_{\text{SYN023}}$ represents the geometric mean concentration of RVNA on Day 8 post-dose in the test group and GMC_{HRIG} represents the geometric mean concentration of RVNA on Day 8 post-dose in the control group with a type I error of 0.025 (one-sided).

RVNA concentrations on Day 8 will be summarized for each treatment group with median, minimum, maximum, geometric mean, 95% CI of geometric mean,

and geometric coefficient of variation. The RVNA concentration at each scheduled visit for each subject is the geometric mean of the duplicate results.

In addition, with the treatment group and the study site used as fixed variables, the mean and standard error of adjusted RVNA (log-transformed) concentrations in two groups will be summarized using analysis of variance, and the ratio of RVNA geometric mean concentrations, 95% CI, and P-value in two groups will be calculated at the two-sided 0.05 level.

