1.1.2 Secondary Objectives

- To demonstrate that the geometric mean RVNA concentration for SYN023 is superior to the geometric mean RVNA concentration for HRIG on Study Day 4;
- To demonstrate that the geometric mean RVNA AUEC1-15 for SYN023 is superior to the geometric mean RVNA AUEC1-15 for HRIG;
- To demonstrate that the Study Day 99 geometric mean RVNA concentration for SYN023 recipients is not inferior to the geometric mean RVNA concentration for HRIG recipients;
- To demonstrate that the percentage of subjects with RVNA concentration ≥ 0.5 IU/mL on Study Day 99 in SYN023 recipients is not inferior to the percentage of recipients with RVNA concentration ≥ 0.5 IU/mL for HRIG;
- To describe the ratio of RVNA GMC in the SYN023 plus Rabies Vaccine group to the HRIG plus Rabies Vaccine group at each time point for subjects in the Per Protocol Set and the Intent-to-Treat Set;
- To describe the ratio of the geometric mean concentrations of RVNA at each time point in SYN023 recipients divided by the geometric mean concentrations of RVNA in HRIG recipients in the Per-protocol and Intent-to-Treat Populations;
- To describe the effects of increasing BMI on RVNA concentrations in SYN023 recipients;
- To evaluate the safety of SYN023 in SYN023 recipients.

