2.5 Subgroup Analysis

If the number of subjects in each subgroup is sufficient, the primary endpoint will be analyzed by the following subgroups:

- 1) Study sites
- 2) Sex
- 3) Age groups (18-59 years, 60 years and older)

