2.6 Pooling of Study Sites

All data of the study sites are pooled for a direct integrated analysis, except efficacy analysis, where study sites are as the covariate.

3 Statistical Analysis

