3.1.3 Demographics and Baseline Characteristics

The demographics and baseline characteristics of subjects will be summarized descriptively based on the PPS and SS by pre-defined groups respectively. Demographics and baseline characteristics will be tabulated.

Demographics:

Categorical variables: sex (male, female), ethnic group (Han, Zhuang, Yi, Hani, Miao, others), and age grouping (18-59 years, 60 years and older).

Continuous variable: age.

Baseline characteristics:

Categorical variables:

- BMI (< 18.5 kg/m², 18.5-24.0 kg/m², ≥ 24.0 kg/m²)
- Type of category III exposure
- Animal causing the wound
- Wound site
 - Category of wound site (high risk, low risk)
- Wound amount
 - Category of wound amount (single wound, multiple wounds)
- Are post-exposure wound cleaning and disinfection performed as required
- Is local anesthesia performed for cleaning and disinfecting the wound
- Did the subject get bitten by animals susceptible to rabies virus during the past 6 months
- Did the subject received any prior/concomitant vaccines 14 days prior to enrollment to the study
- RVNA grouping (RVNA < 0.1 IU/mL and RVNA ≥ 0.1 IU/mL) on Study Day 1

Continuous variable:

Height, weight, body mass index (BMI), and duration from rabies virus exposure to investigational product injection.

It is defined as high-risk if the wound site is any of the head, neck, face, left upper limb, right upper limb; and low-risk for the other parts. Duration of rabies virus exposure to investigational product injection time (h) = investigational product injection time – rabies virus exposure time.

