3.2.2.1 GMC of RVNA on Days 4, 15, 43, 99, 183, 365 Post-Dose

The primary analysis, subgroup analysis, and sensitivity analysis are performed using the same methods as that used for RVNA on Day 8 post-dose. In addition, mean RVNA versus time profiles (linear and semi-logarithmic) and scatter plots of BMI versus RVNA at each scheduled visit post-baseline will be created with scheduled sampling time points.

3.2.2.2 Positive Rate of RVNA on Days 4, 8, 15, 43, 99, 183, and 365 Post-Dose

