3.2.2.3 AUEC₁₋₁₅ of RVNA GMC post-dose

The AUEC₁₋₁₅ of RVNA GMC will be calculated using the trapezoidal method. The primary analysis, subgroup analysis, and sensitivity analysis will be performed using the same method as that used for RVNA on Day 8 post-dose.

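### The RVNA models adjust for site only; prespecifying age, sex and BMI as covariates could recover modest precision on AUEC1-15

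*SAP*

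**What the plan says.** SAP 3.2.1.1.1 compares log-transformed Day 8 RVNA between arms by analysis of variance, "with the treatment group and the study site used as fixed variables". SAP 2.6 pools site data "except efficacy analysis, where study sites are as the covariate". The other RVNA means inherit the model. For the remaining GMC time points, including Day 99, SAP 3.2.2.1 states: "The primary analysis, subgroup analysis, and sensitivity analysis are performed using the same methods as that used for RVNA on Day 8 post-dose". For AUEC1-15, SAP 3.2.2.3 says that the primary, subgroup and "sensitivity analysis will be performed using the same method as that used for RVNA on Day 8 post-dose". Protocol 13.5.3 likewise names only treatment group and site.

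The candidate covariates are already collected. Protocol 11.3 records birth date, gender, height and weight at screening. SAP 3.1.3 lists age and sex under demographics, and its continuous baseline variables are "Height, weight, body mass index (BMI), and duration from rabies virus exposure to investigational product injection". Sex and age group are subgroup factors (SAP 2.5 and 3.2.1.1.2). BMI has its own secondary objective in SAP 1.1.2, "To describe the effects of increasing BMI on RVNA concentrations in SYN023 recipients", but the only analysis given for it is a set of scatter plots (SAP 3.2.2.1).

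**The concern.** Any variation in log RVNA or log AUEC1-15 that age, sex or BMI explains stays in the error term under a treatment-plus-site model and widens the confidence interval for the ratio. Body size is a plausible source of spread: SYN023 and HRIG are dosed per kilogram, while each vaccine dose is a fixed 0.5 mL (protocol 10.6.2). Randomisation is stratified by site alone, so chance imbalance in the three variables is possible, and the per-protocol set removes subjects after randomisation.

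AUEC1-15 is where this could matter. It needs 900 of the 1,000 subjects, far more than any other powered test, and SAP 3.4 reports that the per-protocol set has not reached the planned size. The SAP's response is an exploratory analysis in a wider set that readmits some subjects with detectable baseline RVNA. Covariate adjustment would recover some precision without changing the population.

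**Working it through.** **Inputs** (SAP 1.3.3, item 4): expected AUEC1-15 ratio 1.4755, margin 1.1, CV 142%, one-sided alpha 0.025, power 90%, 3:1 allocation, 20% dropout. R², the share of within-arm, within-site log-scale variance explained by age, sex and BMI, is not in the documents. I assume 2% to 20%.

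**1. Reproduce the plan's figures.**
- Log-scale SD: σ = √ln(1 + 1.42²) = 1.0507.
- Distance from the margin: δ = ln(1.4755/1.1) = 0.2937.
- Controls needed: (1.960 + 1.2816)² × 1.0507² × (1 + 1/3) / 0.2937² = 179.3, so 180 controls and 720 evaluable in all. With dropout, 180/0.8 = 225 controls and 4 × 225 = 900 subjects, as stated.
- Power at 1,000: SE = 1.0507 × √(1/250 + 1/750) = 0.0767, and Φ(0.2937/0.0767 − 1.960) = 96.9%, as stated.

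The 96.9% counts all 1,000 subjects as evaluable. With the plan's own 20% loss, 800 remain, SE = 0.0858 and power is 92.8%.

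**2. Add the covariates.** The residual SD becomes σ√(1 − R²). Noncentral-t power for AUEC1-15:

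| Evaluable (SYN023/HRIG) | R² = 0 | 2% | 5% | 10% | 20% |
|---|---|---|---|---|---|
| 800 (600/200) | 92.8% | 93.2% | 93.9% | 95.0% | 96.9% |
| 720 (540/180) | 90.0% | 90.6% | 91.4% | 92.8% | 95.2% |
| 600 (450/150) | 84.1% | 84.9% | 85.9% | 87.7% | 91.1% |

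The log-scale interval narrows by 1 − √(1 − R²): 1.0%, 2.5%, 5.1% and 10.6% at R² of 2%, 5%, 10% and 20%. At R² = 10%, the evaluable number for 90% power falls from 720 to 720 × 0.9 = 648. The three extra terms use three degrees of freedom among several hundred, which does not change these figures at the precision shown.

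The row of 600 illustrates a shortfall. SAP 3.4 gives no count and does not say whether it compares the set with 900 or with 720.

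**3. Check the other mean comparisons.**
- Day 99 GMC: the protocol synopsis gives a ratio of 86.94% and CV 17.32%; the SAP prints the ratio without the percent sign. Then σ = √ln(1 + 0.1732²) = 0.172 and δ = ln(0.8694/0.8) = 0.0832. The noncentral t gives 61 controls; 61/0.8 rounds up to 77, and 4 × 77 = 308, as stated. Power is already 99.996% at 800 evaluable and 99.92% at 600, so the gain is under 0.1 point at any R².
- Day 8: ratio 11.9 against margin 1.2 with CV 120.5% gives σ = 0.947 and δ = ln(11.9/1.2) = 2.294. At 800 evaluable the SE is 0.0773, so power is effectively 100% with or without adjustment.

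**The case against.** The strongest reply is that nothing is wrong. Site is the only stratification factor, the model includes it, the analysis is prespecified in both documents, and type I error is unaffected. That stands: a reader might infer that omitting age, sex and BMI is an error, and the documents do not support that.

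The evidence that these variables predict RVNA is also thin. A subgroup analysis asks whether the treatment ratio varies, not whether the factor explains variance within arms. The BMI objective is descriptive. The dosing argument concerns weight more directly than BMI, and no passage quantifies it. An R² near zero is compatible with the documents, and at 2% the gain is about half a point with 800 evaluable. At that number power already exceeds the 90% target. This also stands, and it limits the claim to precision that may be lost.

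A reader might extend the point to Day 99. At the Day 4 CV of 63.25%, Day 99 GMC power at 800 evaluable would be about 42%, rising only to 50% at R² = 20%. But the plan's Day 99 CV is 17.32%, at which there is nothing to gain. Whether that CV is credible is a separate question, and adjustment would not rescue the test if it were not.

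Finally, AUEC1-15 is last in the SAP 2.4 sequence, behind Day 8, Day 4 and both Day 99 tests. Extra power there has confirmatory value only if all of those succeed.

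What remains against these points is that the downside is negligible and the test that could benefit is the one the SAP itself reports as short of subjects.

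**Conclusion.** The point holds as an optional efficiency gain for AUEC1-15. For an assumed R² of 2% to 20%, power rises by about 0.5 to 4 points at 800 evaluable, 0.6 to 5 points at 720 and 0.7 to 7 points at 600. These figures rest on the plan's ratio, margin and CV for AUEC1-15, on the assumed R², and on evaluable numbers chosen for illustration. The calculation does not cover the Day 99 positive-rate comparison, which is an analysis of proportions. Label: free improvement.

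**What to change.** Before unblinding, amend SAP 3.2.2.3 to specify an ANCOVA on log AUEC1-15 with treatment, site, continuous age, sex and continuous BMI, and derive the ratio and its 95% CI from the adjusted means. For consistency, make the same change in SAP 3.2.1.1.1, which 3.2.2.1 inherits. Keep the treatment-plus-site model as a named sensitivity analysis. State a simple fill for missing height or weight, such as the mean over both arms, so that no subject drops out of the model.

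Because protocol 13.5.3 names only treatment and site, list the change in SAP section 5, which does not mention it now. SAP 3.4 shows that per-protocol numbers were already known when it was written, so record that the covariates were fixed while blinded. Protocol 8.2.5 already requires the SAP to be signed before unblinding.

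The cost is SAP wording and three model terms, with no new data and no extra subjects.

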3.2.1.1.2 Subgroup Analysis

The following subgroup analyses will be performed for RVNA on Day 8 post-dose. With treatment group used as a fixed variable, and the adjusted ratios and standard errors of the two groups will be calculated using analysis of variance, and the ratios and 95% CIs of the two groups by site will be summarized.

- Study sites
- Sex
- Age groups (18-59 years, 60 years and older)
- RVNA grouping (SS only) on Study Day 1: RVNA < 0.1 IU/mL and RVNA \geq 0.1 IU/mL

3.2.1.1.3 Sensitivity Analysis

Based on the PPS only, a sensitivity analysis of the primary efficacy endpoints will be performed after excluding the deviations in post-dose RVNA from geometric mean concentration \pm 3 times the geometric SD using the same method as the primary analysis.

3.2.1.2 Incidence and Survival Rate of Subjects with Rabies within 99 Days and 1 Year Post-Dose

The incidence and survival rate of subjects with rabies within 99 days and 1 year post-dose will be described by number and percentage of subjects.

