1.3.3 Sample Size

Primary study hypothesis:

The test group is superior to the control group in the geometric mean concentration of RVNA on Day 8 post-dose (the lower limit of the 95% confidence interval (CI) of the geometric mean concentration of RVNA (test group/control group) > 1.2)

Based on the study hypothesis, the lower limit of the 95% confidence interval (CI) of the geometric mean concentration of RVNA (test group/control group) is > 1.2 , a final sample size of 16 subjects (12 subjects in the test group and 4 subjects in the control group) is required with a type I error of 0.025 (one-sided), a power of

90%, an estimated geometric mean concentration of RVNA (test group/control group) on Day 8 post-dose of 11.9, and a coefficient of variation (CV) of 120.5%, when assigning the subjects to the test group/control group at a ratio of 3:1 and considering a dropout rate of 20%. The current 1000 subjects are sufficient to ensure a 100% power under the same hypothesis.

Secondary study hypothesis:

- 1) The test group is superior to the control group in the geometric mean concentration of RVNA on Day 4 post-dose (the lower limit of the 95% confidence interval (CI) of the geometric mean concentration of RVNA (test group/control group) > 1.2)

Based on the study hypothesis, the lower limit of the 95% confidence interval (CI) of the geometric mean concentration of RVNA (test group/control group) is > 1.2 , a final sample size of 12 subjects (9 subjects in the test group and 3 subjects in the control group) is required with a type I error of 0.025 (one-sided), a power of 90%, an estimated geometric mean concentration of RVNA (test group/control group) on Day 4 post-dose of 13.75, and a CV of 63.25%, when assigning the subjects to the test group/control group at a ratio of 3:1 and considering a dropout rate of 20%. The current 1000 subjects are sufficient to ensure a 100% power under the same hypothesis.

- 2) The test group is non-inferior to the control group in the geometric mean concentration of RVNA on Day 99 post-dose (the lower limit of the 95% confidence interval (CI) of the geometric mean concentration of RVNA (test group/control group) > 0.8)

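### The outlier limits for the per-protocol sensitivity analyses add a unitless geometric SD to a concentration; they should be stated on the log scale, by treatment group and visit

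*SAP*

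**What the plan says.** SAP 3.2.1.1.3 defines a sensitivity analysis, per-protocol set only, that drops outlying RVNA values and repeats the primary analysis. The limits are given by "excluding the deviations in post-dose RVNA from geometric mean concentration" followed by ± and "3 times the geometric SD using the same method as the primary analysis".

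SAP 3.2.2.2.3 has the same rule for the positive-rate analysis. Two sections import it by reference: 3.2.2.1 for the GMC at the other visits ("sensitivity analysis are performed using the same methods as that used for RVNA on Day 8 post-dose") and 3.2.2.3 for AUEC1-15 ("sensitivity analysis will be performed using the same method as that used for RVNA on Day 8 post-dose").

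The analysis being checked is on the log scale. In SAP 3.2.1.1.1, "the mean and standard error of adjusted RVNA (log-transformed) concentrations in two groups will be summarized using analysis of variance". The same section says that "RVNA concentrations on Day 8 will be summarized for each treatment group", with geometric means and a geometric CV.

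The SAP does not define the geometric SD or say that the limits are formed on logs. It also does not say whether they are computed within arm or over both arms. Protocol 13.5.3 contains no outlier rule that would settle this.

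**The concern.** The geometric SD is exp(SD of the logs). It is a ratio, so the meaningful operations are multiplying and dividing by it. Adding three of them to a concentration gives a limit that depends on the unit of measurement and does not match the model being checked. If the term was meant as the SD of the logs, that is unitless too.

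The wording leaves at least three readings: GM ± 3 × GSD as printed, GM ×/÷ GSD³ (the true 3-SD rule on logs), and GM ×/÷ (3 × GSD). Each can also be applied by arm or pooled. Different programmers could reach different analysis sets from one pre-specified sentence. Under the printed reading the analysis would not test the influence of outliers. It could remove a large share of ordinary values and would usually ignore low ones.

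**Working it through.** **Inputs.** SAP 1.3.3 gives, for Day 8, "a coefficient of variation (CV) of 120.5" percent, a ratio of 11.9, a margin of 1.2, 3:1 allocation and 20% dropout. Subjects after dropout: 750 × 0.8 = 600 and 250 × 0.8 = 200. The documents give no Day 8 GMC by arm, so all titre levels below are assumptions. Data are taken as log-normal.

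**Check that the planning CV is a log-normal CV.** Log SD = √ln(1 + 1.205²) = 0.947. Control n = (1.960 + 1.282)² × 0.947² × (1 + 1/3) / [ln(11.9/1.2)]² = 2.4, so 3 control and 9 test. Dividing by 0.8 and rounding up gives 4 + 12 = 16, the SAP's figure.

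**Limits at that CV.** GSD = e^0.947 = 2.578.
- Printed: half-width 3 × 2.578 = 7.73 IU/mL.
- Log scale: factor 2.578³ = 17.14. Share excluded 2(1 − Φ(3)) = 0.27% at any level.
- GM ×/÷ (3 × GSD): factor 7.73. Share excluded 2[1 − Φ(ln 7.73 / 0.947)] = 3.1%.

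**Lower limit, no titre level assumed.** GM − 3 × GSD ≤ 0 whenever GM ≤ 3 × GSD. That is 7.7 IU/mL on Day 8, 5.4 on Day 4 (CV 63.25%, GSD 1.786) and 3.6 on Day 99 (CV 17.32%, GSD 1.188). As GSD ≥ 1, the lower limit is never positive for GM ≤ 3.

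**Share excluded by the printed rule**, planned Day 8 CV. High side: 1 − Φ(ln[(GM + 7.73)/GM] / 0.947). Low side: Φ(ln[(GM − 7.73)/GM] / 0.947) if the limit is positive, otherwise 0.

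| Assumed GM (IU/mL) | Low side | High side | Total | Log-scale rule |
|---|---|---|---|---|
| 1 | 0 | 1.1% | 1.1% | 0.27% |
| 11.9 | 13.4% | 29.9% | 43% | 0.27% |

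Of 600 SYN023 subjects that is about 7 and 259, against 1.6. At GM 11.9 the log SD of the kept values falls from 0.95 to 0.43. Expressing the GM 1 data in mIU/mL raises the share excluded from 1.1% to 99.3%.

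**A matched mean and spread.** Protocol 6.3.4 gives 4.55 ± 1.55 IU/mL on Day 7 for SYN023 without vaccine (± taken as SD). CV = 1.55/4.55 = 0.341, GM = 4.55/√(1 + 0.341²) = 4.31, GSD = 1.393. The printed window is 0.13 to 8.49, excluding 2.0%, all high. The log-scale window is 1.59 to 11.64.

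**Effect on the Day 8 ratio, printed limits.** The mean log of kept values is m + s[φ(a) − φ(b)]/[Φ(b) − Φ(a)], with a and b the standardised log limits.
- *By arm, true ratio 11.9.* At HRIG GM 1 the kept mean logs are 2.258 and −0.028, so the ratio is e^2.286 = 9.8. Over HRIG GMs of 0.1 to 5 the ratio runs from a minimum of about 8.2 (near GM 0.7) to 15.6 (GM 5).
- *Pooled, 3:1 mix.* Log SD = √(0.947² + 0.75 × 0.25 × (ln 11.9)²) = 1.431, GSD 4.18, half-width 12.5. At HRIG GM 5 the pooled GM is 5 × 11.9^0.75 = 32.0, so the window is 19.5 to 44.6. It keeps about 26% of SYN023 values (GM 59.5) and 6.5% of HRIG values. The ratio is 7.3 at HRIG GM 1, 5.6 at GM 2 and 1.16 at GM 5. At GM 5 the lower 95% limit is about 1.02, starting from 600/200 before exclusions.

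**Positive rates.** Even on the log scale, at the planned Day 8 CV, every value below 0.5 IU/mL is excluded once GM exceeds 0.5 × 17.14 = 8.6.

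**The case against.** The strongest reply is that this is notation. A geometric SD is obtained by taking logs, SAP 3.2.1.1.1 works on logs and reports geometric statistics, and a competent programmer may well code GM/GSD³ to GM × GSD³. That is plausible, but the SAP does not say it. The closing reference to the primary method governs the analysis run after exclusion, not how the limits are set. The factor 3 × GSD is also a possible reading.

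Other parts of the reply stand. The percentages describe the printed reading at assumed levels, and 11.9 as a concentration simply corresponds to an HRIG GM of 1. The bridging level comes from subjects without vaccine, whereas everyone here is vaccinated. SAP 2.3.5 treats post-dose values below quantitation as missing, so the log-normal model may overstate the low tail; the quantitation limit is not given, so the amount is unknown.

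A reader might infer that the primary conclusion is in doubt. The documents do not support that. The rule is confined to per-protocol sensitivity analyses, and SAP 3.2 has the main analysis run without it, "with the PPS used for the primary analysis and SS used for the supportive analysis". The opposite inference, that the sensitivity result is safe on any reading, is not supported either, because it needs by-arm limits that the SAP does not specify.

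**Conclusion.** The rule is ill-formed as written and cannot be reproduced from the SAP alone. Severity is minor: the primary test, alpha, hierarchy and sample size are untouched.

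The unit problem and the non-positive lower limit (GM up to 7.7 IU/mL on Day 8) need no assumed titre, only the planned CV. The shares excluded and the ratios after exclusion rest on log-normal data, the planned CV and illustrative GMs. With printed limits by arm, the ratio stays far above 1.2 over the range examined. With printed limits pooled over arms and high titres, the sensitivity analysis could falsely contradict a sound primary result. That is a possibility under one reading, not a forecast.

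The exclusion in SAP 3.2.2.2.3 is a separate weakness. It selects on the titre that defines the positive rate, and moving to the log scale does not cure that.

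**What to change.** Replace the limit in SAP 3.2.1.1.3 with: *exclude values with |ln(RVNA) − mean ln(RVNA)| > 3 SD of ln(RVNA), i.e. outside GM/GSD³ to GM × GSD³, computed by treatment group and visit.* Computing by treatment group matches how SAP 3.2.1.1.1 summarises the titres. The reference in 3.2.2.1 then carries the corrected rule. In 3.2.2.3, state the same form on ln(AUEC).

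In SAP 3.2.2.2.3, either delete the exclusion analysis or keep it labelled as selected on the outcome and not as a robustness check.

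Cost: one sentence in the SAP, a short addition for AUEC1-15, a label or deletion for positive rates, and one line of code. No data collection, sample size or confirmatory analysis changes.
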